4.3 Early Withdrawal of Subjects from the Study

Subjects may withdraw from the study at any time. If a subject withdraws consent, all follow up will stop, however data collected up to that point will still be used. Subjects may be withdrawn from the study for the following reason:

- Patient chooses to withdraw consent

4.3.1 Early Withdrawal of Subjects from Drug

Subjects may be withdrawn from drug early for the following reasons:

CMV disease requiring therapy with valG. Cytomegalovirus disease will be defined as CMV DNA in the blood (viremia) on two or more occasions with clinical and/or pathological confirmation of CMV end-organ disease.

- PI decides that further treatment is not in the best interest of the subject
- Graft failure
- Pregnancy
- Treatment related anaphylaxis

4.3.2 Data Collection and Follow-up for Withdrawn Subjects

Subjects will be followed for 12-18 months post-transplant procedure. Please refer to Table 1 for data points and frequency.

5 Study Procedures

5.1 Subject Recruitment and Screening

Initial contact regarding the research study will be done by the transplant clinical team or clinical research team once notification of treatment date is set. For potential subjects that are receiving a transplant from a living donor, the study team will approach for informed consent prior to transplant surgery. For subjects that receive a transplant from a deceased donor, because of time constraints, the study team may approach the patient after they are placed on the transplant list to introduce the study. Informed consent will then be obtained up to 7 days post-operatively.

5.2 Randomization

The randomization will be done in a 1:1 fashion and will be computer generated.

5.3 Laboratory Testing

Blood is collected in accordance to standard of care procedures for these patients. Left-over blood from the clinical laboratories of subjects will be obtained and tested for CMV and EBV quantitative PCR assay (qPCR), at minimum weekly for the first month and monthly for the first year to year and a half post-KTx. Acyclovir levels will be measured

at 1 month in patients randomized to valA. CMV and EBV IgG and IgM levels will be measured bi-annually for patients who are seronegative until seroconversion after which they will no longer be checked. Safety labs include complete blood counts and basic metabolic panels which will be done for recipients randomized to valA monthly while participating in the study.

If the labs are not being collected at a minimum of weekly for the first month and then monthly for the first year, the study team will collect 10-15mL of blood from the subjects for research procedures.

Half to one core of kidney tissue will be obtained, if available, from all kidney transplant biopsies performed during the first year post-KTx.

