1.4 Dose Rationale and Risk/Benefits

Prior research at the University of Minnesota has shown that valacyclovir 1g every 8 hours for a total daily dose of 3g is well tolerated and was associated with a reduction in EBV excretion (1) in patients with infectious mononucleosis. Subsequently a study done at the University of Minnesota to characterize the pharmacokinetics and explore the pharmacodynamics of acyclovir in plasma and oral washings of 8 subjects with EBV infectious mononucleosis receiving the same daily dose of valacyclovir (3g) as a twice daily dosing of 1500 mg twice daily demonstrated safety and showed that the quantity of EBV DNA in oral washings and blood, and the severity of illness, measured by a graded scale, decreased during treatment (9).

Therefore in order to increase the likelihood of compliance in our patients, we have decided to utilize 1.5g twice a day dosing of valacyclovir and since it was shown to be effective as therapy in the above study, we hypothesize that it will be adequate for anti-viral prophylaxis as intended in this study. The dose will of course be adjusted based on GFR and in pediatric patients based on their weight as detailed in package insert and below.

No major side effects are anticipated since even very high doses of valA (8g/day), for post-KTx CMV prophylaxis were shown to have no severe or treatment-limiting side effects compared to placebo (10).

2 Study Objectives

Primary Objectives:

To compare the effectiveness of valacyclovir (valA) compared valganciclovir (valG) in the prevention of EBV and CMV viremia post-KTx.

To compare the proportion of patients requiring dose reduction or cessation of valA compared to valG due to adverse drug side effects.

Secondary Objective:

To identify the presence and quantity of EBV and CMV in renal tissue biopsies from kidney transplant recipients.

3 Study Design

This is a single-center, prospective, randomized, pilot study of up to 200 kidney transplant recipients from the University of Minnesota Medical Center. Randomization of subjects will be in a 1:1 ratio to receive either ValA or standard of care regimen of ValG. Duration of therapy will be 3-13 months.

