Subjects will be assessed weekly then monthly for medication compliance, as well as assessing adverse events. Subjects will be assessed at their routine clinic visits, or via email/telephone. Subjects will be followed for a total of 12-13 months, or for an additional 30 days after stop of the drug for adverse events.

Blood samples will be collected by using left-over standard of care samples for immunosuppression drug analysis. From these samples, qualitative PCR assay (qPCR) will assess CMV and EBV for up to six months post study drug cessation. Complete blood count and metabolic panels will be collected clinically, and results recorded for this study. CMV and EBV IgG and IgM levels will be measured bi-annually until seroconversion. In the cases where blood is not drawn for clinical purposes at least once a month, 10-15ml of the subject's blood may be collected for this testing for research purposes. Surveillance kidney transplant biopsies are obtained at the time of transplant, 3 months post-transplant, 12 months post-transplant, and as clinically indicated. For the duration of subject study participation, kidney tissue (two to three cores) from any biopsy will be shared with the research team.

Subjects will be followed-up regularly by the research team during the first year post transplant. During these follow-up assessments, the research team will assess drug adherence as well as evaluate side effects. If subjects are seen during a standard of care visit, laboratory values and a review of medical records will also be performed to assess any potential adverse events.

4 Subject Selection and Withdrawal

4.1 *Inclusion Criteria*

- Adult or pediatric kidney transplant recipients
 - Adult cases are defined as patients transplanted and cared for at the University of Minnesota Medical Center, East Bank campus.
 - Pediatric cases are defined as patients transplanted and cared for at the University of Minnesota Masonic Children's Hospital.
- Consent to participate in the study.

4.2 *Exclusion Criteria*

- Documented allergy to valA or valG

- Recipients that are unable to independently understand the consent form.
- Pregnant

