5.4 Schedule of Events

All assessments will be completed during routine clinical visits when feasible. If the participant does not have a scheduled clinic visit, the participant or parent/guardian can choose to receive an email or phone call follow-up of drug adherence and adverse events. Assessments will continue until at least 30 days after last dose of anti-viral.

Visit Schedule	Pre-KTx	KTx	Weekly During Month 1	Monthly through End of Study Period
CBC and BMP ¹ (routine clinical lab)	X		X	X
CMV PCR, EBV PCR ² ([name] research lab)	X		X	X
CMV IgG, EBV IgG & IgM ² ([name] research lab)	X			X ³
Acyclovir levels				X ⁴
Kidney bx tissue ⁵		X		X ³
Medication compliance			X	X ⁶
Adverse Events assessment			X	X ⁶

1 CBCs and BMP are performed routinely in post-transplant patients. If these are not done clinically, we will collect and perform for research safety monitoring

2 PCRs will be run using leftover blood collected clinically. If no leftover blood is available, we will collect a research specimen.

- 3 Month 6 only
- 4. Month 1 only if randomized to valA
- 5. Kidney biopsies are performed routinely during the first year post-transplant. Paraffin-embedded scrolls will be requested from leftover tissue.
- 6. Completed monthly until 1 month after cessation of the treatment

6 Study Drug

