7.1 Primary Study Endpoints

The primary study endpoints are as follows:

1. Incidence and duration of CMV and EBV viremia and magnitude of viremia as measured by area under the viral load-time curve of recipients who become viremic with CMV and/or EBV in the first year post-Ktx.
2. Incidence of subjects developing drug related side effects requiring dose reduction or cessation.
3. Presence of EBV and or CMV in renal tissue (protocol biopsies).

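### Section 5.3 assigns monthly CBC/BMP safety labs to valA recipients and is silent on valG, while Section 5.4 and Section 3 name no arm; one schedule should govern both arms

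*Combined protocol and SAP*

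**What the plan says.** Four places bear on CBC and BMP collection or on the endpoint that it feeds.

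- **Section 5.3 (Laboratory Testing)** defines safety labs as blood counts and metabolic panels, "which will be done for recipients randomized to valA monthly while participating in the study". It has no corresponding sentence for valG. The next paragraph provides for a 10-15 mL research draw, "If the labs are not being collected at a minimum of weekly for the first month and then monthly for the first year"; that provision names no arm but is worded as being for research procedures.
- **Section 5.4 (Schedule of Events)** marks CBC and BMP before transplant, weekly in month 1 and monthly to the end of the study period, with no arm restriction. Footnote 1 reads: "CBCs and BMP are performed routinely in post-transplant patients". It goes on: "If these are not done clinically, we will collect and perform for research safety monitoring".
- **Section 3 (Study Design)** says: "Complete blood count and metabolic panels will be collected clinically, and results recorded for this study". No arm is named.
- **Sections 2 and 7.1** make tolerability a primary question. The second primary objective is "To compare the proportion of patients requiring dose reduction or cessation of valA compared to valG due to adverse drug side effects", and the second listed primary endpoint is "Incidence of subjects developing drug related side effects requiring dose reduction or cessation".

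Section 6.9 gives blinding as not applicable.

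**The concern.** A comparison of side effects between arms is fair only if the arms are examined with the same intensity. This matters most for haematologic toxicity. Sections 1, 1.1 and 1.3 rest much of the case for valA on its causing less leucopenia than valG, and a cytopenia without symptoms is found on a blood count, not by asking the patient.

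The endpoint is also an action: the dose is reduced or the drug is stopped. If a CBC is not drawn, a low count may go unseen and the dose change may never happen, so later review of the records would not recover the event. Section 5.4 allows adherence and adverse events to be followed by email or telephone when there is no clinic visit, and such contact cannot find an asymptomatic low count. Because treatment is open label, staff know the arm when they decide whether a missed lab has to be made up. A rule that makes it up in one arm only would tilt a primary comparison.

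**Working it through.** The plan states no figure on this point, so there is none to reproduce. The check is a comparison of the passages, followed by the direction of any bias.

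**Step 1: the rules side by side.**

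| Source | Arm covered | Frequency | Missed routine lab |
|---|---|---|---|
| Section 5.3, safety-lab sentence | valA named; valG not mentioned | Monthly | Not addressed |
| Section 5.3, research-draw paragraph | No arm named | Weekly in month 1, then monthly for the first year | Research draw, but unclear whether it covers safety labs or only the PCR samples |
| Section 5.4 table and footnote 1 | No arm named | Pre-transplant, weekly in month 1, then monthly to end of study | Collected and performed by the study |
| Section 3 | No arm named | Not stated | Not addressed for CBC/BMP specifically |

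The safety-lab sentence of Section 5.3 therefore differs from Section 5.4 in two ways: the arm named, and monthly against weekly testing in month 1. No order of precedence is given.

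**Step 2: is a valA-only reading of Section 5.3 plausible?** Yes. Earlier in the same paragraph, the acyclovir level is limited to patients randomized to valA, and there the limit is intended: the Section 5.4 footnote reads "Month 1 only if randomized to valA". A coordinator who meets nearly the same phrase for CBC/BMP could reasonably read it the same way.

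**Step 3: is it the only reading?** No. The word *only* does not appear in the safety-lab sentence. The Section 5.4 table flags the acyclovir level as valA-specific and puts no such flag on CBC/BMP. The sentence could be an added assurance for the investigational arm rather than a withholding of labs from valG.

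**Step 4: direction of bias if Section 5.3 is followed.** Let a and g be the true proportions with a side-effect-driven dose reduction or cessation in valA and valG. Let l be the part of g that would be triggered only by a laboratory finding, and m the fraction of that part lost because a missed CBC was not made up. Assume that missed labs in valA are fully made up. Then

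observed difference (valA minus valG) = a − (g − l × m) = (a − g) + l × m.

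The shift, l × m, is zero or positive, so it makes valA look worse relative to valG than it is.

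**Step 5: size.** Neither l nor m is in the documents. No dose-reduction rate is given for either drug, and no achieved lab frequency by arm. If footnote 1 is followed in both arms, m should be close to zero and so should the shift.

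**The case against.** The strongest reply is that the protocol, read as a whole, already schedules equal testing. The Section 5.4 table is the more detailed statement, names no arm, and carries an explicit make-up rule. Section 3 agrees with it. Routine post-transplant labs apply to everyone, valG dosing is itself tied to GFR (Section 6.2), adverse events are assessed on one schedule in both arms (Section 5.4), and they are sought at every contact (Section 8.1). This is one centre, so different sites cannot adopt different readings. For harm to follow, a routine valG lab must be missed, footnote 1 must not be applied, and the cytopenia must be one that would have led to a dose change and was not caught at the next draw.

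Most of this stands. A reader might infer from Section 5.3 that laboratory toxicity would be looked for unequally, or that nothing else evens out detection in an open-label trial. The documents support neither statement, because Sections 3 and 5.4 provide for CBC/BMP without regard to arm.

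A reader might also try to size the bias from Section 1.3, which cites a list of valG adverse events in at least 20% of patients. Losing an assumed 10-30% of 20% would give 20% × 0.10 = 2 points to 20% × 0.30 = 6 points. That is not an estimate of bias in this endpoint. The list includes diarrhoea, fever, nausea, vomiting and tremor as well as cytopenias; the figure is not a rate of dose reduction or cessation; and nothing in the documents supports the missed fraction.

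The objection does not remove the contradiction. The two sections give different rules for the same tests, and the arm-specific wording of Section 5.3 has a natural valA-only reading.

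**Conclusion.** The concern holds as an internal inconsistency with a possible, unquantified effect on a primary comparison. Section 5.3 names valA alone for monthly CBC/BMP; Sections 5.4 and 3 name no arm. If Section 5.3 is what staff follow, missed routine labs would be made up in valA and not in valG, valG cytopenias could be under-detected, and the comparison of dose reduction or cessation would most likely be biased against valA.

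This rests on three conditions: that some routine valG labs are missed, that Section 5.3 rather than footnote 1 is applied to them, and that some of the missed results would have led to a dose change. Because these labs are routine after transplant, the number of affected draws may be small. The documents do not allow the size to be computed. The point is worth correcting because the endpoint is primary, the trial is unblinded, and the remedy costs almost nothing.

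**What to change.** Reconcile Section 5.3 with Section 5.4 so that there is one CBC/BMP rule: the schedule in the Section 5.4 table, and the make-up rule in its footnote 1, apply to all recipients in both arms. Replacing only the words that name valA would not be enough, because Section 5.3 would still say monthly where the table has weekly testing in month 1. It is simplest for Section 5.3 to refer to the table for arm, frequency and duration. The research-draw paragraph should also say whether it covers safety labs or only the virology samples.

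The cost is a short wording amendment and an occasional CBC/BMP draw in valG patients whose routine labs were missed. Section 5.4 already commits to those draws, so no new procedure is added.

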5.4 Schedule of Events

All assessments will be completed during routine clinical visits when feasible. If the participant does not have a scheduled clinic visit, the participant or parent/guardian can choose to receive an email or phone call follow-up of drug adherence and adverse events. Assessments will continue until at least 30 days after last dose of anti-viral.

Visit Schedule	Pre-KTx	KTx	Weekly During Month 1	Monthly through End of Study Period
CBC and BMP ¹ (routine clinical lab)	X		X	X
CMV PCR, EBV PCR ² ([name] research lab)	X		X	X
CMV IgG, EBV IgG & IgM ² ([name] research lab)	X			X ³
Acyclovir levels				X ⁴
Kidney bx tissue ⁵		X		X ³
Medication compliance			X	X ⁶
Adverse Events assessment			X	X ⁶

1 CBCs and BMP are performed routinely in post-transplant patients. If these are not done clinically, we will collect and perform for research safety monitoring

2 PCRs will be run using leftover blood collected clinically. If no leftover blood is available, we will collect a research specimen.

- 3 Month 6 only
- 4. Month 1 only if randomized to valA
- 5. Kidney biopsies are performed routinely during the first year post-transplant. Paraffin-embedded scrolls will be requested from leftover tissue.
- 6. Completed monthly until 1 month after cessation of the treatment

6 Study Drug

6.1 Description

Valacyclovir is a nucleoside analogue DNA polymerase inhibitor capsule of 500 mg.

Valganciclovir is a cytomegalovirus nucleoside analogue DNA polymerase inhibitor tablet of 450 mg.

6.2 Treatment Regimen

Dosing of valG and valA will be based on level of renal function assessed by glomerular filtration rate (GFR).

Table 2: valA (valAcyclovir) dosing based on GFR

GFR	> 50ml/min	30-49ml/min	10-29ml/min	< 10ml/min
Adults	1500mg BID	1000mg BID	500mg BID	500mg QD
Children	20mg/kg BID	15mg/kg BID	7.5mg/kg BID	7.5mg/kg QD

Table 3: valG (valGanciclovir) dosing based on GFR

GFR	\geq 60ml/min	40-59ml/min	25-39ml/min	10-24 ml/min	< 10ml/min
Adults	900mg QD	450mg QD	450mg QOD	450 mg twice weekly	Hold dose
Children	7 x BSA x Creatinine Clearance (CrCl) (calculated by modified Schwartz formula and Cockcroft-Gault for less than and equal to 17 years of age respectively; max 900 QD; max CrCl 150 mL/min/1.73 mL/m²)				

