10.2	AUDITING AND INSPECTING.....	23
11	ETHICAL CONSIDERATIONS	23
11.1	INFORMED CONSENT	23
12	STUDY FINANCES.....	23
12.1	FUNDING SOURCE.....	23
12.2	CONFLICT OF INTEREST.....	24
13	PUBLICATION PLAN	24
14	REFERENCES	25

List of Abbreviations

AE	Adverse Event
BID	twice daily
BMP	basic metabolic panel
CBC	complete blood count
CFR	Code of Federal Regulations
CMV	cytomegalovirus
CRF	Case Report Form
DSMB	Data and Safety Monitoring Board
DSMP	Data and Safety Monitoring Plan
EBV	Epstein-Barr virus
FDA	Food and Drug Administration
GCP	Good Clinical Practice
HIPAA	Health Insurance Portability and Accountability Act of 1996
ICH	International Conference on Harmonization
IDS	Investigational Drug Services
IRB	Institutional Review Board
KTx	kidney transplant
PCR	Polymerase Chain Reaction
PHI	Protected Health Information
SAE	Serious Adverse Event
QD	once daily
QOD	every other day
valA	valAcyclovir
valG	valGanciclovir

Study Summary

Title	Valacyclovir versus Valganciclovir for Post-transplant Cytomegalovirus/Epstein-Barr Virus Prophylaxis: A Randomized Controlled Trial
Short Title	ValA vs ValG for Post-transplant CMV/EBV Prevention
Protocol Number	11.0
Phase	Pilot
Methodology	Randomized Control Trial
Study Duration	36 months
Study Center(s)	Single-Center
Objectives	To compare the effectiveness of valacyclovir (valA) to valganciclovir (valG) in the prevention of EBV and CMV viremia post-kidney transplant.
Number of Subjects	Total of 200
Diagnosis and Main Inclusion Criteria	Adult and pediatric kidney transplant recipients
Study Product, Dose, Route, Regimen	Valacyclovir Dose: 500-1500mg bid Oral
Duration of administration	3-12 months dependent on treatment assignment and donor and recipient viral serostatus in accordance with standard of care.
Reference therapy	Valganciclovir Oral
Statistical Methodology	Incidence of viremia will be compared using a two-sided Fisher exact test and viral load-time curve areas will be compared using a Mann-Whitney test. A p-value of ≤ 0.05 will be considered significant.

1 Introduction

Infections are now a leading cause of death and morbidity in kidney transplant recipients. Herpes viruses such as Epstein-Barr virus (EBV) and cytomegalovirus (CMV) are particularly troublesome.

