6.3 Duration of Therapy

Duration of therapy is dependent on donor and recipient antibody status.

Adult subjects will be treated with their assigned study drug (ValA or ValG) for **three months**, unless the donor is antibody positive and the recipient is antibody negative (D+R-) to CMV/EBV, then patient will get six months of prophylaxis.

Pediatric transplant recipients will be treated for **twelve months except** if both the donor and the recipient are antibody negative (**D- R-**) for both CMV and EBV, subjects will be treated for **three months**.

Patients that are randomized to ValA that develop CMV disease or CMV viremia X2 may discontinue ValA and begin standard of care treatment with ValG. At that time they will continue research related follow up but ValA use is up to the discretion of the treating physician. At that time all protocol directed safety follow up will be discontinued; however, outcomes will be followed until month 12.

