6.5 Preparation and Administration of Study Drug

After randomization, the treating investigator will order the treatment following this protocol dosing schema (see Tables 2 and 3). Commercial supply of ValA and ValG will be dispensed to the subjects.

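### Table 2 prints no maximum for paediatric valacyclovir, so above 75 kg (GFR >50) or 66.7 kg (lower columns) it assigns more drug than the adult row

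*Combined protocol and SAP*

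**What the plan says.** Section 6.2 gives the valA regimen in "Table 2: valA (valAcyclovir) dosing based on GFR". Its Adults row is 1500 mg BID (GFR >50), 1000 mg BID (30-49), 500 mg BID (10-29) and 500 mg QD (<10). Its Children row is 20, 15 and 7.5 mg/kg BID and 7.5 mg/kg QD, with no upper limit in any column.

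Table 3, for valganciclovir (valG), does limit the paediatric dose. Its Children row includes the words "less than and equal to 17 years of age respectively; max 900 QD".

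Section 6.5 makes the tables operative: "the treating investigator will order the treatment following this protocol dosing schema (see Tables 2 and 3".

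Two other places bear on a possible limit. Section 1.4 says the dose is adjusted "in pediatric patients based on their weight as detailed in package insert and below". The Study Summary gives "Valacyclovir Dose: 500-1500mg bid Oral", without separating adults from children or one GFR band from another.

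**The concern.** A mg/kg rule without a maximum eventually passes the fixed adult dose. Patients heavy enough for that can fall in the Children row. Section 4.1 defines paediatric cases by treating hospital, with no age or weight limit, and Table 3's Children row refers to 17 years of age. A maximum for the comparator but none for the study drug looks like an oversight.

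What is at stake is dosing safety in a small subgroup. The relative excess is greater in the three lower GFR columns, where the protocol itself reduces the adult dose. Section 6.6 lists acute renal failure and nervous system effects among the rare reactions to valA, without saying at what dose. Exposure can be long: section 6.3 treats paediatric recipients for twelve months unless donor and recipient are both antibody negative for both viruses, against three or six months for adults.

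**Working it through.** The plan states no crossover weight, so there is no figure to reproduce. All doses come from Table 2. The weights are illustrative, because the documents give no paediatric weights.

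**Step 1: crossover weight.** Within each column both rows have the same dosing frequency, so it cancels. Crossover weight = adult mg per dose / child mg per kg per dose.

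- GFR >50: 1500/20 = 75 kg
- GFR 30-49: 1000/15 = 66.7 kg
- GFR 10-29 and <10: 500/7.5 = 66.7 kg

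**Step 2: excess above the crossover.** Child dose = weight × mg/kg, compared with the adult dose in the same column.

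| GFR | Adult dose | Child, 70 kg | Child, 80 kg | Child, 100 kg |
|---|---|---|---|---|
| >50 | 1500 mg BID | 1400 (-6.7%) | 1600 (+6.7%) | 2000 (+33%) |
| 30-49 | 1000 mg BID | 1050 (+5%) | 1200 (+20%) | 1500 (+50%) |
| 10-29 | 500 mg BID | 525 (+5%) | 600 (+20%) | 750 (+50%) |
| <10 | 500 mg QD | 525 (+5%) | 600 (+20%) | 750 (+50%) |

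Down the columns, the excess per dose is 100, 200, 100 and 100 mg at 80 kg, and 500, 500, 250 and 250 mg at 100 kg. It is therefore larger at reduced GFR in percent, but not consistently in mg.

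**Step 3: rounding.** Section 6.1 describes valA as a 500 mg capsule. Assume rounding to the nearest 500 mg; no rounding rule is stated. A rounded dose then exceeds the adult dose once the calculated dose passes the midpoint to the next unit:

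- GFR >50: 1750/20 = 87.5 kg
- GFR 30-49: 1250/15 = 83.3 kg
- GFR 10-29 and <10: 750/7.5 = 100 kg

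On this assumption no 70 or 80 kg dose exceeds the adult dose. Above the new thresholds the excess is a whole unit: at 90 kg and GFR 30-49, 1350 mg becomes 1500 mg against 1000 mg (+50%).

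**Step 4: the Study Summary range read as a ceiling.** A limit of 1500 mg BID would bind at 1500/20 = 75 kg (GFR >50), 1500/15 = 100 kg (30-49) and 1500/7.5 = 200 kg (10-29). It removes the excess only in the first column. At 80 kg and GFR 30-49, 1200 mg lies inside the range but above the adult 1000 mg. The range also does not describe the Children row: 20 mg/kg is below 500 mg for any child under 500/20 = 25 kg, and the last column is once daily.

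**The case against.** The strongest objection is that section 1.4 names the package insert alongside the table. If the insert carries a maximum, the protocol arguably already includes it and the gap is editorial. That stands as a possibility. The insert is not in the documents, however, and section 6.5 sends the prescriber to the tables. If a cap exists, Table 2 is where it needs to be printed.

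Second, at GFR >50 the concern is weak. Section 1.4 gives 1.5 g twice daily as the chosen dose, the Study Summary's upper figure agrees, and sections 1.3 and 1.4 report tolerance of 8 g/day, against 3.2 g/day for an 80 kg child. This stands for that column. The tolerance statement mentions neither children nor reduced GFR.

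Third, 500 mg units could absorb the excess at 70 and 80 kg. A reader might take the +5% and +20% as doses that would be delivered. The documents do not support that: they are what the table assigns before any rounding. Nor do the documents establish rounding, and section 1.2 describes a 25 or 50 mg/mL suspension for children who cannot take a solid form.

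Fourth, per kg of body weight a heavy child may get less than a light adult: a 60 kg adult at GFR >50 gets 1500/60 = 25 mg/kg, against 20 mg/kg. That is true, but it does not explain why the table gives an adult of the heavy child's own weight less.

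Fifth, there are safeguards. The blood counts and "basic metabolic panels which will be done for recipients randomized to valA monthly" (weekly in month 1 under section 5.4) and the investigator's power to stop drug (section 4.3.1) all help. The acyclovir level is a single measurement, "Month 1 only if randomized to valA", and no text ties it to a dose change.

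Finally, reach is small. The Introduction gives 120 paediatric recipients from October 2003 to December 2009 (75 months), or 120/75 × 12 = 19.2 a year. If that rate held for the full 36-month study and every child enrolled, 1:1 allocation would put about 57.6/2 = 29 on valA. Only those above the crossover weights matter.

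**Conclusion.** The point holds as a minor safety correction. Table 2 taken literally assigns a paediatric patient above 75 kg (GFR >50) or 66.7 kg (lower columns) more valA than an adult in the same column. On the assumed rounding to 500 mg, the thresholds become about 83 kg (GFR 30-49), 87.5 kg (GFR >50) and 100 kg (the two lowest columns). Neither the Study Summary range nor any other text in the documents clearly removes the excess in the lower columns. The main uncertainty is the insert, which may contain a cap.

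Two stronger conclusions might be inferred, and the documents support neither. One is that heavy children will in practice be overdosed or harmed: the number affected is unknown and probably small, and the insert, rounding and monitoring could each prevent or limit it. The other is that the trial's results would be distorted. Dose reduction or cessation for side effects is a primary endpoint in section 7.1, but no effect on it, on viremia or on power has been shown.

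**What to change.** Print Table 2's Children row with a maximum in each column equal to the adult dose:

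- GFR >50: 20 mg/kg BID, maximum 1500 mg per dose
- GFR 30-49: 15 mg/kg BID, maximum 1000 mg per dose
- GFR 10-29: 7.5 mg/kg BID, maximum 500 mg per dose
- GFR <10: 7.5 mg/kg QD, maximum 500 mg

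If the package insert gives a lower maximum, print that instead. The values need clinical confirmation.

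The cost is a one-row amendment to the IRB and a check of the valA order for any enrolled child above 66.7 kg. It adds no patients, visits or tests.
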